10.5.2 Secondary Efficacy Analysis

The secondary efficacy endpoints will be analyzed similar to the primary efficacy endpoint.

The change from baseline to the exit visit in each of the FACE-Q™ modules overall Rasch-transformed scores will be analyzed using paired t-test (or Wilcoxon signed-rank test if normality assumptions are not met).

10.5.4 Missing Data

Missing data strategy will be documented in the study SAP.

10.5.5 Adverse Events

AEs will be coded using MedDRA version 17.0 or higher, and presented by system organ class and preferred term. Treatment-emergent AEs will also be summarized by SAEs, AE severity, AE leading to treatment or study early termination, and relationship to study drugs/devices. Summary tables will be presented by the study treatment drug.

10.6 INTERIM ANALYSES AND DATA MONITORING

No interim analysis is planned.

10.7 DETERMINATION OF SAMPLE SIZE

In the 2 US pivotal trials for BELKYRA® (ATX-101-11-22 and ATX-101-11-23), 79.1% and 77.9% of subjects, respectively, demonstrated a ≥ 1 grade improvement in the CR-SMFRS 12 weeks following the final treatment. In the VOLUMA-002 study, the responder rate defined as the percentage of subjects whose overall mid-face volume deficit improved (i.e., decreased) by ≥ 1 point from baseline based on the average of the 2 blinded Evaluating Investigators'

Clinical Study Protocol: CMO-MA-FAS-0513

assessments at Month 6 using the 6-point Mid-Face Volume Deficit Scale, was 85.6% at Month 6.

In this study, as BELKYRA® and VOLUMA™ will be administered sequentially, the estimated responder rate for the jawline severity is set lower at 78.0%.

The sample size will provide reasonable precision of the estimations of the parameters of interests. With 40 subjects, the half-width of the 95% confidence interval for the proportion of subjects who show ≥ 1 -point improvement from baseline on the ALJDS compared to baseline assessment at the final study visit (after last VOLUMA™ treatment received) is 14.0% assuming the improvement rate is 78%. To account for 20% study drop-out rate and/or subjects who may not continue for the VOLUMA™ treatment, 50 subjects will be enrolled.

The sample size calculation was performed using the PASS 2008 software for one single proportion.

10.8 CHANGES IN THE CONDUCT OF THE STUDY OR PLANNED ANALYSIS

Any changes to the conduct or planned analyses will be handled via protocol or SAP amendment, respectively.

11 REGULATORY, ETHICAL, AND LEGAL OBLIGATIONS

11.1 DECLARATION OF HELSINKI

The Investigator will ensure that this study is conducted in accordance with the most recent revision of the Declaration of Helsinki.

11.2 GOOD CLINICAL PRACTICE

The study will be conducted according to the study protocol and to Standard Operating Procedures that meet the guidelines provided by the International Conference on Harmonization (ICH) for Good Clinical Practice in clinical studies.

11.3 INDEPENDENT ETHICS COMMITTEES

Before implementing this study, the protocol, the proposed subject informed consent forms, and other information for the subjects must be reviewed by a properly constituted committee or committees responsible for approving clinical studies. The IEC/IRB written, signed approval letter/form must contain approval of the designated Investigator, the protocol (identifying protocol title, date and version number), the subject informed consent form (date, version), and any other subject facing documents.

11.4 REGULATORY AUTHORITY APPROVAL

The study is utilizing all products as per their licensed usage and indications. No regulatory approval will be required.

Clinical Study Protocol: CMO-MA-FAS-0513

11.5 PROTOCOL COMPLIANCE

The Investigator is responsible for compliance with the protocol at the investigational site. The Investigator is also responsible for reporting all issues of protocol non-compliance to the respective IEC/IRB and to the Sponsor. A representative of the Sponsor will make frequent contact with the Investigator and his/her research staff and will conduct regular monitoring visits at the site to review subject and study device accountability records for compliance with the protocol, e.g., subject eligibility criteria, volume of product injected, procedures performed, and follow-up visit schedule.

11.6 INFORMED CONSENT

Written informed consent is to be obtained from the subject prior to any study-related procedures or change in treatment. Privacy-related documentation will also be obtained from each subject prior to enrollment into the study, in accordance with relevant country and applicable local privacy requirements.

All subjects will be required to participate in the consent process. During the consent process, the person obtaining consent will inform the subject of all elements of informed consent. The Investigator must ensure that the subject is given full and adequate oral and written information about the nature, purpose, possible risk and benefit of the clinical trial. Subjects must also be notified that they are free to withdraw from the clinical trial at any time without prejudice to future care. The subject should be given the opportunity to ask questions and allowed time to consider the information provided.

If the ICF is revised for any reason (e.g., protocol amendment or new safety data), the revised ICF must be reviewed and approved by the IEC/IRB. The revised ICF is not considered effective until approved by the IEC/IRB. All subjects currently enrolled in the clinical trial must sign the revised ICF. Subjects enrolled in the clinical trial after the revised ICF has been approved by the IEC/IRB will sign the revised version.

11.7 SUBJECT CONFIDENTIALITY AND DISCLOSURE

A report of the results of this study may be published or sent to the appropriate health authorities in any country in which the study drug may ultimately be marketed, but the subject's name will not be disclosed in these documents. The subject's name may be disclosed to the Sponsor of the study, Allergan, or the governing health authorities or the US Food and Drug Administration (FDA) if they inspect the study records. Appropriate precautions will be taken to maintain confidentiality of medical records and personal information.

In accordance with Health Insurance Portability and Accountability Act requirements, additional purposes of this study include the following: to publish anonymous subject data from the study and to create and maintain a data repository.

11.8 SPONSOR MONITORING OF STUDY DOCUMENTATION

A representative of the Sponsor will monitor the study on a periodic basis. The determination of the extent and nature of monitoring will be based on considerations such as

Clinical Study Protocol: CMO-MA-FAS-0513

the objective, purpose, design, complexity, size, and endpoints of the study. This will be detailed in the Study Monitoring Plan.

Authorized representatives of Allergan or regulatory authority representatives will conduct on-site visits to review, audit and copy study-related documents. These representatives will meet with the Investigator(s) and appropriate staff at mutually convenient times to discuss study-related data and questions.

11.9 STUDY DOCUMENTS

The Investigator must maintain source documents for each subject in the study, including all demographic and medical information etc., and keep a copy of the signed and dated informed consent forms. All information on the eCRFs must be traceable to these source documents in the subject's file.

11.10 COLLECTION OF STUDY DATA

This study will be conducted in compliance with the US FDA Code of Federal Regulations (21 CFR Part 11). The Investigator is responsible for ensuring that study data are properly recorded on each subject's eCRFs and related documents. An Investigator who has signed the protocol signature page shall sign for the eCRFs to attest that the observations and findings are recorded on the eCRFs correctly and completely. The eCRFs are to be submitted to Allergan in a timely manner at the completion of the study, or as otherwise specified by Allergan.

The data reported on the eCRFs shall be derived from source documents and be consistent with these source documents, and any discrepancies shall be explained in writing. Any change or correction to data reported on an eCRF shall be dated, initialed and explained, if necessary, and shall not obscure the original entry (i.e., an audit trail shall be maintained); this applies to both written and electronic changes and corrections.

11.11 ARCHIVING OF STUDY DOCUMENTS

All study-related correspondence, subject records, consent forms, subject privacy documentation, records of the distribution and use of all investigational products, and copies of eCRFs should be maintained on file. Allergan-specific essential documents are to be retained until at least 2 years after the last approval of a marketing application in an ICH region and until there are no pending or contemplated marketing applications in an ICH region or at least 2 years have elapsed since the formal discontinuation of clinical development of the investigational product. These documents are to be retained for a longer period, however, if required by the applicable regulatory requirements or if needed by Allergan.

11.12 DISCLOSURE OF INFORMATION

This study will be registered and results posted on www.clinicaltrials.gov. Allergan, as the Sponsor, has proprietary interest in this study. Authorship and manuscript composition will reflect joint cooperation between study Investigators and Allergan personnel. Authorship will be established prior to the writing of the manuscript. As this study involves multiple

Clinical Study Protocol: CMO-MA-FAS-0513

centers, no individual publications will be allowed prior to completion of the final report of the multicenter study except as agreed with Allergan.

Clinical Study Protocol: CMO-MA-FAS-0513

[figure not shown]

13 APPENDICES

[figure not shown]

[figure not shown]

[figure not shown]

[figure not shown]

[figure not shown]

[figure not shown]

[figure not shown]

[figure not shown]

[figure not shown]

[figure not shown]

[figure not shown]

[figure not shown]

[figure not shown]

[figure not shown]

[figure not shown]

[figure not shown]

[figure not shown]

[figure not shown]

[figure not shown]

[figure not shown]

[figure not shown]

[figure not shown]

[figure not shown]

[figure not shown]

[figure not shown]

[figure not shown]

[figure not shown]

[figure not shown]

APPENDIX 14 VERSION HISTORY

Version Number	Version Date	Author	Changes Made
1.0	26Jul2017	[REDACTED]	Original version
1.1	17Aug2017	[REDACTED]	
Non-substantial changes:
 
 1. [REDACTED] 2. Sections 5.1.1, BELKYRA – added statements regarding number of vials contained in kits 3. Sections 5.1.4, Treatment Assignments – added statements regarding partially used kits and unopened vials/syringes; added statements regarding number of vials contained in kits 4. Section 5.2.1 Storage – added instruction for inventory at vial and syringe level 5. Section 5.3.2 VOLUMA – specified that cannula used for VOLUMA treatment is per Allergan guidance.
1.2	26Sep2017	[REDACTED]	
Non-substantial changes:
 
 1. [REDACTED] 2. [REDACTED] 3. [REDACTED] 4. [REDACTED] 5. [REDACTED] 6. [REDACTED] 7. [REDACTED] 8. [REDACTED] 9. [REDACTED] 10. [REDACTED] 11. [REDACTED] 12. [REDACTED] 13. [REDACTED] 14. [REDACTED] 15. [REDACTED] 16. [REDACTED] 17. [REDACTED] 18. [REDACTED] 19. [REDACTED] 20. [REDACTED] 21. [REDACTED] 22. [REDACTED] 23. [REDACTED] 24. [REDACTED] 25. [REDACTED] 26. [REDACTED] 27. [REDACTED] 28. [REDACTED] 29. [REDACTED] 30. [REDACTED] 31. [REDACTED] 32. [REDACTED] 33. [REDACTED] 34. [REDACTED] 35. [REDACTED] 36. [REDACTED] 37. [REDACTED] 38. [REDACTED] 39. [REDACTED] 40. [REDACTED] 41. [REDACTED] 42. [REDACTED] 43. [REDACTED] 44. [REDACTED] 45. [REDACTED] 46. [REDACTED] 47. [REDACTED] 48. [REDACTED] 49. [REDACTED] 50. [REDACTED] 51. [REDACTED] 52. [REDACTED] 53. [REDACTED] 54. [REDACTED] 55. [REDACTED] 56. [REDACTED] 57. [REDACTED] 58. [REDACTED] 59. [REDACTED] 60. [REDACTED] 61. [REDACTED] 62. [REDACTED] 63. [REDACTED] 64. [REDACTED] 65. [REDACTED] 66. [REDACTED] 67. [REDACTED] 68. [REDACTED] 69. [REDACTED] 70. [REDACTED] 71. [REDACTED] 72. [REDACTED] 73. [REDACTED] 74. [REDACTED] 75. [REDACTED] 76. [REDACTED] 77. [REDACTED] 78. [REDACTED] 79. [REDACTED] 80. [REDACTED] 81. [REDACTED] 82. [REDACTED] 83. [REDACTED] 84. [REDACTED] 85. [REDACTED] 86. [REDACTED] 87. [REDACTED] 88. [REDACTED] 89. [REDACTED] 90. [REDACTED] 91. [REDACTED] 92. [REDACTED] 93. [REDACTED] 94. [REDACTED] 95. [REDACTED] 96. [REDACTED] 97. [REDACTED] 98. [REDACTED] 99. [REDACTED] 100. [REDACTED]

1.3	21Nov2017	[REDACTED]	
Non-substantial changes:
 
 1. Protocol Summary (Secondary Endpoints) and Sections 7.2.1 and 10.4.2.1 Allergan Loss of Jawline Definition Scale– added Independent Reviewer assessment for the ALJDS 2. Section 4.4.1.1 Anesthesia – clarified “area of injection” such that anesthetic interventions apply to treatment or biopsy 3. Section 7.1.6 Photographic Imaging – specified imaging to also be completed “within 60 minutes after VOLUMA treatment” for consistency with Table 1.1 4. Section 7.1.7 Biopsy – changed biopsy sample size from “3-4mm” to “2mm”. Changed location of biopsy excision site from “2cm” to “approximately 1.5cm” 
[REDACTED]

2.0	xxFeb2018	[REDACTED]	
Substantial Changes:
 
[REDACTED]
 
[REDACTED]
 
 3. Section 6.1.4 Subject Enrollment – deleted subject status terms and definitions 
[REDACTED]
 
[REDACTED]
 
 6. Section 10.1.1 Analysis Populations; Protocol Summary, Statistical Methods – modified analysis set titles and definitions to be consistent with non-randomized trials. 
Non-substantial Changes:
 
[REDACTED]
 
[REDACTED]
 
[REDACTED]

6.2.1 Primary Efficacy Analysis16

6.2.2 Secondary Efficacy Analyses16

[REDACTED]

6.3 SubGroup Analyses 19

7. Safety Analyses.....19

7.1 Exposure to Study Treatment(s)..... 19

7.2 Adverse Events 20

7.3 Serious Adverse Events 21

7.4 Other Safety Analysis..... 22

7.5 Pregnancy 22

7.6 Subgroup Analyses for Safety Variables 22

8. Pharmacokinetic, Biomarker, Genomic, or Immunogenicity Data Analyses
.....22

9. Health Outcomes Data Analyses22

10. Interim Analyses22

11. Data Collected but not Analyzed.....23

12. References.....23

13. Appendices24

Summary of Changes

Version Number	Version Date	Author	Changes Made
1.0	14-Jan-2019	[REDACTED]	Initial Version
2.0	29-Aug-2019	[REDACTED]	Changes from V1.0 to V2.0 include: 
 • Revisions to section 6.2.3.3 - Image Analysis • Revisions to section 7.4 - Other Safety Analysis • [REDACTED]
3.0	21-Feb2020	[REDACTED]	Changes from V2.0 to V3.0 include: 
 • Addition of section 6.3 - SubGroup Analyses • [REDACTED]

1. Introduction

The purpose of this Statistical Analysis Plan (SAP) is to provide details of the data analyses as outlined in the study protocol dated on March 21, 2018 and titled “A Prospective, Open-label Study to Evaluate Sequential Treatment with BELKYRA® and Juvéderm® VOLUMA with Lidocaine (VOLUMA) for Overall Improvement in Jawline Contour”.

This SAP should be reviewed in conjunction with the study protocol. In case of any discrepancies in the statistics section between the protocol and the SAP, the SAP will supersede the protocol, as the SAP is intended to be more precise and specific. Any amendment to the SAP will be made prior to database lock. Any additional analyses performed but not described in the final SAP or deviations from the final SAP will be documented in the clinical study report.

This study is a Phase IV, post-marketing study sponsored by Allergan. It is a prospective, open-label, multi-center, interventional, drug and medical device study to evaluate the combined effectiveness of sequential BELKYRA treatments of convexity or fullness associated with submental fat and VOLUMA to restore volume along the mandible in enhancing the overall contour of the jawline. This post-marketing study includes an exploratory endpoint for a Biopsy Sub-study to evaluate histological changes from baseline to after the final BELKYRA treatment.

Approximately 50 male and female subjects will be treated in the study, out of which approximately 10 subjects are expected to participate in the Biopsy Sub-study. Data collection on participants may continue from a minimum of 12 weeks and up to approximately 64 weeks, depending on the number of BELKYRA injections needed and participation in the Biopsy Sub-study.

There will be no interim analysis. One final analysis is planned for this study. The final analysis will be performed upon the completion of the study. Database lock will be executed for the final analysis.

2. Primary Study Objectives and Design

2.1 Study Design

This Phase IV trial is a prospective, open-label, multi-center, interventional, drug and medical device, post-marketing study. Each subject will act as his/her own control. Subjects will attend a minimum of 6 and maximum of 18 visits.

Approximately 50 male and female subjects will be treated. Approximately 10 of them are expected to participate in the Biopsy Sub-study.

All subjects will sign an informed consent form (ICF) at the Screening Visit (Visit 1). Eligible subjects will undergo treatment with BELKYRA injected into subcutaneous pre-platysma fat tissue in the submental area (Visit 2.1/Day 0). Seven days after the initial BELKYRA treatment (Visit 3.1), the subject will return to the clinic for a safety evaluation. Eight weeks after BELKYRA treatment, the submental profile will be evaluated by the investigator and the subject. If further BELKYRA intervention is required to achieve the desired result, subjects may receive up to 5 optional BELKYRA treatments (Visits 2.2 to 2.6), for a maximum of 6 treatments including the initial required treatment. Subjects who receive optional BELKYRA treatments will be contacted by telephone 7 days after treatment for safety evaluation (Visits 3.2 to 3.6). The submental profile will be assessed as described 8 weeks after each BELKYRA treatment, and a decision made if further BELKYRA treatments are desired.

When the investigator and the subject agree that no further BELKYRA intervention is required to achieve the desired result, the subject may receive VOLUMA treatment (Visit 4). Fourteen days after VOLUMA treatment, subjects will return to the clinic (Visit 5) and the investigator will assess whether a VOLUMA touch up treatment is to be performed. All subjects will attend a final exit visit (Visit 6) which is 4 weeks after the last VOLUMA treatment (Visit 4 if no touch-up done or Visit 5, if touch-up was performed).

Subjects will have the option of participating in a Biopsy Sub-study. Participation in the sub-study is voluntary and will not affect the subject's eligibility to participate in the main study. Biopsy samples will be collected from the submental region at 2 time points: Visit B1 will occur at least 4 weeks before the first BELKYRA treatment (at Visit 2.1); Visit B2 will occur 8 weeks after the last BELKYRA treatment and at least 4 weeks prior to VOLUMA treatment (at Visit 4). Histological changes from baseline to after final BELKYRA treatment(s) will be evaluated.

2.2 Primary Objective

The primary objective of the study is to evaluate the combined effectiveness of sequential BELKYRA treatments on submental fat (SMF) and VOLUMA on restoring mandible volume to enhance the overall contour of the jawline.

2.3 Secondary Objectives

- To evaluate the investigator's and subject's assessment of aesthetic improvement of the lower face and jawline.

3. Analysis Populations and Data Conventions

3.1 Analysis Populations

To adequately describe the statistical analyses, three analysis populations are defined as follows:

- Full Analysis Set (FAS): Consists of all subjects who received BELKYRA.
- Evaluable Set (ES): Consists of the FAS subjects who received both BELKYRA and VOLUMA and a post-treatment efficacy assessment at Visit 6 (Exit Visit).
- Safety Analysis Set (SAS): Consists of all subjects who consented to participation. Includes subjects who are defined as FAS subjects and those subjects who underwent biopsy procedure but did not receive the BELKYRA treatment. This population will be used for safety analyses.

Unless specified otherwise, the FAS will be used for summary of subject disposition, demographics, baseline characteristics, and for efficacy analyses of endpoints that are

assessed up to the end of BELKYRA treatment; the Evaluable Set will be used for the efficacy analyses of endpoints that are assessed at the final study visit, and the Safety Analysis Set will be used for safety analyses.

Note that in the context of the SAP (including the TFL mockup shells), subjects in the safety analysis set are called safety subjects, and subjects in the evaluable set are called evaluable subjects. Also, the terms of full analysis set, safety analysis set and evaluable set mentioned in the protocol are used interchangeably with full analysis population, safety analysis population and evaluable population respectively.

[REDACTED]

[REDACTED]

[REDACTED]

[REDACTED]

[REDACTED]

[REDACTED]

3.3 Data Conventions

3.3.1 Study Day

For each subject, the reference start date (also referred to as Day 0 per the protocol) is the date when the subject receives his/her first injection of BELKYRA treatment at Visit 2.1. Study day will be calculated using visit date and the reference start date as follows: (1) study day = (visit date – reference start date + 1), for any visit date \geq reference start date. (2) study date = (visit date – reference start date), for any visit/time point date < reference start date.

3.3.2 Imputation for Missing Measurement or Assessment Data

There is no imputation for missing values for post-baseline measurements or assessments. All data summaries and analyses of post-baseline data will be conducted using observed cases.

3.3.3 Imputation for Missing or Partially Missing Dates

Any partial or missing dates occurring between the enrollment date and the exit date will be queried to obtain the full date prior to imputation.

3.3.3.1 For assigning treatment-emergent AEs (TEAEs), and prior and concomitant medications

The followings rules will be applied for partial or missing start dates:

- If the day is missing, the first day of the given month will be used unless the month and year are the same as the month and year of enrollment, in which case the date of enrollment will be used. Note that the enrollment date for the subjects of the biopsy sub-study is at Visit B1, instead of Visit 2.1.
- If the day and month are missing, the 1st of January will be used unless the year is the same as the year of enrollment, in which case the date of enrollment will be used.
- If the whole date is missing, the date of enrollment will be used.

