7.2 Adverse Events

Adverse events (AE) will be coded using MedDRA v20.1 or later to give a PT and a SOC term for each event.

An AE is defined as any untoward medical occurrence in a clinical investigational patient administered a pharmaceutical (investigational) product or any undesirable physical, psychological or behavioral effect experienced by a subject during his/her participation in a study, in conjunction with the use of the device and which does not necessarily have to have a causal relationship with this treatment.

All AEs will be included in by-subject AE listings. A separate listing will be created with all the distinct levels of SOC and PT, and the verbatim investigator description reported in the study. Sorting will be by earliest observed SOC, PT within SOC and then verbatim description.

A treatment-emergent adverse event (TEAE) is a post-baseline AE where (i) there is no pre-treatment AE of the same MedDRA primary SOC and PT; or (ii) the maximum severity during the post-baseline period is greater than the maximal severity of any pre-treatment AE of the same MedDRA primary SOC and PT during the enrollment visit. Note that the post-baseline period of the study starts upon the initiation of the BELKYRA treatment at Visit 2.1/Day 0.

Partial or missing AE start dates will be handled as per Section 3.3.3.1.

An overall summary of frequency count and the binomial incidence rate with associated 95% CIs will be presented to describe the incidents of TEAEs. Note that 95% CIs of the binomial incidence rate will be presented for the overall summary analyses of TEAEs, but not for the by-visit analyses. Percentages and corresponding 95% CIs will be displayed to 1 decimal place.

Each type of AE will be tabulated by SOC and PT within SOC. The SOC and PT within SOC will be sorted by descending frequency. Number of subjects with percentage and number of events will be presented based on SOC and PT.

The incidence of all TEAEs by SOC and PT will be presented for the following categories:

- Any TEAE
- Any TEAE related to BELKYRA
- Any TEAE related to VOLUMA
- Any TEAE related to anesthesia
- Any TEAE related to study procedure
- Any TEAE related to BELKYRA/VOLUMA and leading to discontinuation of treatment with BELKYRA/VOLUMA
- Any TEAE by maximum severity

The following listing will be provided:

- Listing of all TEAE

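### In biopsy sub-study subjects, SAP 3.3.3.1 can impute an incomplete start date of a post-BELKYRA adverse event to before first treatment, so the event leaves the TEAE tables (minor)

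*SAP*

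**What the plan says.** SAP 7.2 fixes the cut-off for treatment emergence: "Note that the post-baseline period of the study starts upon the initiation of the BELKYRA treatment at Visit 2.1/Day 0". For incomplete dates it points elsewhere: "Partial or missing AE start dates will be handled as per Section 3.3.3.1".

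SAP 3.3.3.1 gives three rules for start dates:

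- Day missing: "If the day is missing, the first day of the given month will be used unless the month and year are the same" as those of enrolment, in which case the enrolment date is used.
- Day and month missing: "If the day and month are missing, the 1st of January will be used unless the year is the same" as that of enrolment, in which case the enrolment date is used.
- Nothing known: "If the whole date is missing, the date of enrollment will be used".

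The note attached to the first rule defines enrolment for the sub-study: "Note that the enrollment date for the subjects of the biopsy sub-study is at Visit B1, instead of Visit 2.1". The contrast implies that all other subjects are anchored at Visit 2.1.

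SAP 2.1 and Protocol 3.1 place Visit B1 at least 4 weeks before first BELKYRA. SAP 3.3.3 requires incomplete dates to be queried before any imputation.

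**The concern.** For subjects outside the sub-study, the imputation anchor and the TEAE cut-off are the same day. For biopsy subjects they are at least 28 days apart, and the anchor is the earlier of the two. Nothing visible in SAP 3.3.3.1 or 7.2 moves a date that could be on or after treatment up to Visit 2.1, and neither section uses the AE end date or causality for this purpose. The case-by-case clause in SAP 3.3.3.2 concerns time intervals, not TEAE status.

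An event that began after first BELKYRA can therefore receive a pre-treatment date and be left out of the TEAE tables, including the table of events related to BELKYRA. There is also a knock-on effect. Limb (i) of the TEAE definition requires that "there is no pre-treatment AE of the same MedDRA primary SOC and PT". The misdated event becomes such a pre-treatment AE, so a later, fully dated event of the same term also fails to qualify unless it is more severe (limb (ii)). For truly post-treatment events in these subjects, the error can only lower the TEAE counts.

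**Working it through.** No figure in the documents bears on this, so the rules were applied as written.

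**Rule.** An event is handled as pre-treatment if its imputed start date is earlier than Visit 2.1.

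**Worked example** (illustrative dates). B1 is 14 May 2018, Visit 2.1 is 11 June 2018 (28 days later), and true onset is 14 June 2018.

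| Known parts | Imputed, anchor B1 | Status | Imputed, anchor Visit 2.1 | Status |
|---|---|---|---|---|
| June 2018 | 1 June | pre-treatment | 11 June | TEAE |
| 2018 | 14 May | pre-treatment | 11 June | TEAE |
| none | 14 May | pre-treatment | 11 June | TEAE |

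When only the day is missing, the failure usually runs through the 1st of the month and not through B1. The exception clause protects the month of B1, not the month of Visit 2.1. With a 28-day gap the two visits share a calendar month for only about 8% of B1 dates. Year-only dates in the year of Visit 2.1 go to B1, or to 1 January if B1 was in the previous year. Blank dates go to B1.

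**Share of truly post-treatment events imputed before Visit 2.1.** This is an exact enumeration over 365 B1 dates, with gaps of 28 to 42 days and onset spread evenly over the stated days after first BELKYRA:

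| Missing | 7 days | 28 days | 84 days | 448 days |
|---|---|---|---|---|
| Day | 0.868 | 0.523 | 0.175 | 0.033 |
| Day and month | 0.989 | 0.960 | 0.884 | 0.406 |
| Whole date | 1.00 | 1.00 | 1.00 | 1.00 |

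With the anchor at Visit 2.1, every cell is 0. For day-missing dates the share is 0.94 when onset is in the calendar month of Visit 2.1, 0.001 for days 28-83, and 0 from day 84.

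**Expected number misclassified** = events × proportion still missing the day × share. The documents give neither of the first two. Assume 50 events in the roughly 10 subjects and 1-5% still missing the day after query.

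Subjects may have up to 6 treatments at least 8 weeks apart. If events cluster in the week after each treatment, in equal numbers, only those after the first treatment are at material risk, so the share is about 0.868/k for k treatments:

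- k = 2: 0.434; 50 × 0.01 × 0.434 = 0.22 to 50 × 0.05 × 0.434 = 1.1
- k = 3: 0.289; 0.14 to 0.72
- k = 6: 0.145; 0.07 to 0.36
- Onset spread evenly over 448 days: 50 × 0.01 × 0.033 = 0.02 to 50 × 0.05 × 0.033 = 0.08
- Every event within 7 days of a first treatment: at most 50 × 0.05 × 0.868 = 2.2

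These counts cover day-missing dates only and leave out the knock-on effect. Each subject whose only event is lost lowers an incidence by 1/50 = 2 percentage points if the denominator is 50.

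**The case against.** The best defence is that few dates will ever reach this rule. Incomplete dates are queried first, Protocol 9.1.1.1 has AEs asked about at every visit, and onset is a required AE field (Protocol 9.1.1.2). The first week, where the day-missing share is highest, ends with an in-clinic safety visit. Year-only and blank dates, which fail most often, are also the least likely to survive query. All of this stands, and it is why the expected count is low.

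A B1 anchor also has a rationale: AEs are collected from consent and the biopsy is itself a study procedure. That supports B1 for events known to precede BELKYRA. It does not support B1 for events that may have followed it.

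A reader might infer more than the documents support:

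- *That the SAP contradicts itself.* It does not. SAP 3.3.3.1 is a dating convention and SAP 7.2 is applied to the resulting date, so both can be followed together. The convention simply does not fit the cut-off.
- *That every incomplete date goes to B1.* Day-missing dates usually go to the 1st of the month. Day-missing events in months after that of Visit 2.1, and year-only events in later years, are not affected.
- *That TEAEs are understated across the trial.* The problem is confined to biopsy subjects. For the others, the implied Visit 2.1 anchor can if anything count a pre-treatment event as a TEAE.
- *That events vanish from the report.* They do not: "All AEs will be included in by-subject AE listings".

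Finally, parts of the SAP between 3.1 and 3.3 and much of Protocol section 6 are redacted, and the table shells are not available. The absence of a safeguard can be stated only for the visible text.

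**Conclusion.** The point holds, as a minor one. For about 10 of 50 subjects the imputation convention does not fit the TEAE cut-off, and for post-treatment events it errs in the non-conservative direction. The mechanism follows from the text alone. Its size does not, because the documents give no AE count and no rate of incomplete dates.

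Under the assumptions shown, the expected number is probably below about one event: 0.07 to 1.1 with clustering after 2 to 6 treatments, and 0.02 to 0.08 with even spread. The 2.2 figure needs every event to start within a week of a first treatment and should not be taken as typical. No efficacy endpoint is affected.

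**What to change.** In SAP 3.3.3.1, for AE start dates only and for subjects who received BELKYRA, use the date of first BELKYRA (Visit 2.1) as the anchor in place of the enrolment date. Exception: if the known date parts or the AE end date show onset before Visit 2.1, keep the current rule with Visit B1 as the anchor for biopsy subjects. Keep Visit B1 for biopsied subjects who never received BELKYRA. Leave the medication anchor unchanged, since concomitant status in SAP 5.3 does not depend on when a medication started, and leave the duration rules in SAP 3.3.3.2 as they are.

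The work is one added rule and one derivation, made before database lock as SAP section 1 requires for amendments.

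The price is that some undated events that truly arose between B1 and Visit 2.1, such as biopsy-site reactions, would count as TEAEs. With onset spread evenly over that gap, and before any help from end dates, this is 52% of day-missing dates at a 28-day gap and 35% at 42 days, 94-96% of year-only dates, and 100% of blank dates. That is the conservative direction for safety tables.

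An event could also carry one start date for TEAE status and another for duration. The SAP already allows this, using the 1st of the month for one purpose and the 15th for the other.
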